### 7.3 PLANNED ANALYSES

#### Analysis sets

Statistical analyses will be based on the following analysis sets:

- Treated set (TS): The treated set includes all subjects who were randomized and treated with at least one dose of study drug. The treated set will be used for safety analyses.
- Pharmacokinetic parameter analysis set (PKS): This set includes all subjects in the treated set (TS) who provide at least one PK endpoint that was defined as primary or secondary and was not excluded due to a protocol deviation relevant to the evaluation of PK or due to PK non-evaluability (as specified in the following subsection 'Pharmacokinetics'). Thus, a subject will be included in the PKS, even if he

Proprietary confidential information © 2019 Boehringer Ingelheim International GmbH or one or more of its affiliated companies

contributes only one PK parameter value for one period to the statistical assessment. Descriptive and model based analyses of PK parameters will be based on the PKS.

Adherence to the protocol will be assessed by the trial team. Important protocol deviation (IPD) categories will be suggested in the IQRM plan, IPDs will be identified no later than in the Report Planning Meeting, and the IPD categories will be updated as needed.

### Pharmacokinetics

The pharmacokinetic parameters listed in [Section 2.1](#) for drug BI 1358894 will be calculated according to the relevant SOP of the Sponsor ([001-MCS-36-472](#)).

Plasma concentration data and parameters of a subject will be included in the statistical pharmacokinetic (PK) analyses if they are not flagged for exclusion due to a protocol deviation relevant to the evaluation of PK (to be decided no later than in the Report Planning Meeting) or due to PK non-evaluability (as revealed during data analysis, based on the criteria specified below). Exclusion of a subject's data will be documented in the CTR.

Relevant protocol deviations may be

- Incorrect trial medication taken, i.e. the subject received at least one dose of trial medication the subject was not assigned to
- Incorrect dose of trial medication taken
- Use of restricted medications

Plasma concentrations and/or parameters of a subject will be considered as non-evaluable, if for example

- The subject experienced emesis that occurred at or before two times median  $t_{max}$  of the respective treatment (Median  $t_{max}$  is to be determined excluding the subjects experiencing emesis),
- A predose concentration is  $>5\%$   $C_{max}$  value of that subject
- Missing samples/concentration data at important phases of PK disposition curve

Plasma concentration data and parameters of a subject which is flagged for exclusion will be reported with its individual values but will not be included in the statistical analyses.

Descriptive and inferential statistics of PK parameters will be based on the PKS.

Only concentration values within the validated concentration range and actual sampling times will be used for the calculation of pharmacokinetic parameters. Concentrations used in the pharmacokinetic calculations will be in the same format provided in the bioanalytical report, (that is, to the same number of decimal places provided in the bioanalytical report).

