Apathy	0 (0.0)	0 (0.0)	1 (16.7)	0 (0.0)	0 (0.0)	0 (0.0)	0 (0.0)	0 (0.0)
Metabolism and nutrition disorders	1 (7.7)	0 (0.0)	0 (0.0)	0 (0.0)	0 (0.0)	0 (0.0)	0 (0.0)	0 (0.0)
Decreased appetite	1 (7.7)	0 (0.0)	0 (0.0)	0 (0.0)	0 (0.0)	0 (0.0)	0 (0.0)	0 (0.0)

Proprietary confidential information © 2019 Boehringer Ingelheim International GmbH or one or more of its affiliated companies

Table 1.2.1.5: 2      Frequency [N (%)] of subjects with adverse events treated with  
BI 1358894 – 1402-0001 FE part

System Organ Class, Preferred Term	BI 50mg (fast) (N=8)	BI 50mg (fed) (N=8)	BI 100mg (fast) (N=12)	BI 100mg (fed) (N=12)
Total with adverse events	7 (87.5)	7 (87.5)	8 (66.7)	6 (50.0)
Nervous system disorders	7 (87.5)	7 (87.5)	8 (66.7)	5 (41.7)
Headache	7 (87.5)	6 (75.0)	7 (58.3)	4 (33.3)
Dizziness	3 (37.5)	2 (25.0)	3 (25.0)	2 (16.7)
Disturbance in attention	2 (25.0)	0 (0.0)	0 (0.0)	0 (0.0)
Head discomfort	0 (0.0)	1 (12.5)	0 (0.0)	0 (0.0)
Paraesthesia	1 (12.5)	0 (0.0)	0 (0.0)	0 (0.0)
Skin and subcutaneous tissue disorders	0 (0.0)	2 (25.0)	0 (0.0)	1 (8.3)
Pruritus generalised	0 (0.0)	1 (12.5)	0 (0.0)	0 (0.0)
Rash macular	0 (0.0)	1 (12.5)	0 (0.0)	0 (0.0)
Skin reaction	0 (0.0)	1 (12.5)	0 (0.0)	0 (0.0)
Acne	0 (0.0)	0 (0.0)	0 (0.0)	1 (8.3)
General disorders and administration site conditions	1 (12.5)	0 (0.0)	0 (0.0)	2 (16.7)
Fatigue	1 (12.5)	0 (0.0)	0 (0.0)	2 (16.7)
Musculoskeletal and connective tissue disorders	0 (0.0)	1 (12.5)	2 (16.7)	0 (0.0)
Musculoskeletal chest pain	0 (0.0)	1 (12.5)	0 (0.0)	0 (0.0)
Arthralgia	0 (0.0)	0 (0.0)	1 (8.3)	0 (0.0)
Back pain	0 (0.0)	0 (0.0)	1 (8.3)	0 (0.0)
Gastrointestinal disorders	1 (12.5)	1 (12.5)	0 (0.0)	0 (0.0)
Flatulence	0 (0.0)	1 (12.5)	0 (0.0)	0 (0.0)
Nausea	1 (12.5)	0 (0.0)	0 (0.0)	0 (0.0)
Infections and infestations	0 (0.0)	0 (0.0)	1 (8.3)	0 (0.0)
Nasopharyngitis	0 (0.0)	0 (0.0)	1 (8.3)	0 (0.0)

Dose Groups 2, 3 and 6 already have sample results available up to 192 h and, therefore, were used to calculate PK parameters dependent on the terminal rate constant (lambda z). Half-life as calculated from these 3 DGs is around 45 to 52 h (gMean) and appears to be independent of dose.

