Proprietary confidential information © 2019 Boehringer Ingelheim International GmbH or one or more of its affiliated companies

**Table 1.2.1.5: 3** Summary of gMean (gCV %) PK parameters of 3, 6, 10, 25, 50, 100 and 200 mg BI 1358894 administered under fasted conditions [SRD part; clinical trial 1402-0001]

Dose Group:	DG1	DG2	DG3	DG4	DG5	DG6	DG7
Dose [mg], formulation	3 mg, tablet	6 mg, tablet	10 mg, tablet	25 mg, tablet	50 mg, tablet	100 mg, tablet	200 mg, tablet
	fasted	fasted	fasted	fasted	fasted	fasted	fasted
						Without #	
	N=6	N=6	N=6	N=6	N=6	N=6	N=5
AUC0-24 [nmol*h/L]	166 (15.7)	269 (28.9)	400 (13.9)	937 (43.4)	1670 (32.8)	919 (1130)	2210 (58.4)
AUC0-24/D [nmol*h/L/mg]	55.5 (15.7)	44.8 (28.9)	40.0 (13.9)	37.5 (43.4)	33.4 (32.8)	9.19 (1130)	22.1 (58.4)
AUC0-72 [nmol*h/L]	261 (17.9)	445 (31.6)	651 (14.5)	1780 (31.1)	3040 (27.7)	2000 (1320)	5010 (40.4)
AUC0-72/D [nmol*h/L/mg]	87.1 (17.9)	74.1 (31.6)	65.1 (14.5)	71.2 (31.1)	60.9 (27.7)	20.0 (1320)	50.1 (40.4)
AUC0-tz [nmol*h/L]	288 (18.5)	569 (32.7)	861 (17.7)	2380 (29.7)	4170 (26.2)	2520 (2670)	7120 (37.9)
AUC0-∞ [nmol*h/L]	353* (25.1)	603 (33.6)	930 (20.4)	2580 (30.2)	4530 (24.5)	3000 (1570)	7730 (39.8)
AUC0-∞/D [nmol*h/L/mg]	118* (25.1)	100 (33.6)	93.0 (20.4)	103 (30.2)	90.6 (24.5)	30.0 (1570)	77.3 (39.8)
Cmax [nmol/L]	27.6 (30.0)	35.9 (33.8)	59.7 (13.4)	84.2 (44.2)	183 (56.3)	94.3 (735)	206 (72.8)
Cmax/D [nmol/L/mg]	9.20 (30.0)	5.99 (33.8)	5.97 (13.4)	3.37 (44.2)	3.66 (56.3)	0.943 (735)	2.06 (72.8)
tmax [h]	2.0 (1-4)	2.5 (1-5)	1 (1-3)	5 (1-6)	1 (0.5-2.5)	2.25 (1-6)	3 (1-6)
							5 (1-8)

tmax median (range), D Dose-normalized, DG dose group,

sensitivity analysis without subject who had substantially lower BI 1358894 plasma concentrations

\* values are based on planned sampling time points up to 96 h only

Proprietary confidential information © 2019 Boehringer Ingelheim International GmbH or one or more of its affiliated companies

Table 1.2.1.5: 4

Summary of gMean (gCV %) PK parameters of 50 mg and 100 mg BI 1358894 administered under fasted conditions and after a high calorie, high fat meal [relative BA food effect part; clinical trial 1402-0001]

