## 1.2.2 Residual Effect Period

The Residual Effect Period (REP) of BI 1358894 is approximately 14 days. This is the period after the last dose with measurable drug levels and/or pharmacodynamic effects is still likely to be present.

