### 3. DESCRIPTION OF DESIGN AND TRIAL POPULATION

#### 3.1 OVERALL TRIAL DESIGN AND PLAN

The study will be performed as a randomised, open-label, single-dose, incomplete blocks crossover trial in healthy male subjects in order to compare the test treatments TF2 in fasted state (C and E) to the reference treatment TF1 in fed state (A) to investigate the relative bioavailability of tablet formulation. Additionally, it will evaluate the food effect on test treatments. The test treatments will be one single dose of 100 mg BI 1358894 of the TF2 in a fed state (B) and in the fasted state (C) and TF2 in the fed state (D) and in the fasted state (E). The reference treatment to compare the bioavailability of tablet formulations will be one single dose of 100 mg BI 1358894 of the TF1 (A) administered to subjects in the fed state.

Twenty-four subjects will be randomly allocated to 12 treatment sequences. For details, refer to [Section 4.1](#).

The planned 24 subjects to be included in the study will be assigned to three cohorts, each consisting of eight subjects. The cohorts will be treated at least one week apart. The second and third cohort will be dosed after a careful review by the Investigator of the safety data from all subjects in the preceding cohort(s).

Table 3.1: Treatment sequences

Blocks/Sequences	1	2	3	4	5	6	7	8	9	10	11	12
Period 1	A	D	E	C	A	E	B	C	B	D	C	A
Period 2	B	A	B	A	E	D	C	E	D	C	B	E
Period 3	C	B	A	D	C	A	D	B	E	E	A	D

There will be a washout period of at least 17 days between the treatments, i.e. the dose in the first treatment period and the dose in the second treatment period are separated by at least 17 days. In each subject, an assessment of safety laboratory, vital signs, ECG and AEs will be conducted on the last day of the preceding period prior to next dosing. These data will be reviewed by the Investigator to confirm the eligibility of the subject before the following dosing.

An overview of all relevant trial activities is provided in the [Flow Chart](#). For visit schedule and details of trial procedures at selected visits, refer to [Sections 6.1](#) and [6.2](#), respectively.

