#### 3.2 DISCUSSION OF TRIAL DESIGN, INCLUDING THE CHOICE OF CONTROL GROUPS

For relative bioavailability trials, the crossover design is preferred because of its efficiency: since each subject serves as his own control, the comparison between formulations is based on an intra-subject comparison, thus removing inter-subject variability from the comparison between formulations [[R94-1529](#)]. The incomplete blocks design was chosen for this study

Proprietary confidential information © 2019 Boehringer Ingelheim International GmbH or one or more of its affiliated companies

instead of a full 5x5 crossover design due to the long apparent terminal half-life of BI 1358894 (between 54.8 and 82.5 h) resulting in a long washout period (17 days).

The open-label treatment is not expected to bias results, since the study endpoints are derived from measurement of plasma concentrations of BI 1358894, which are provided by a bioanalytical laboratory that is blinded to treatment allocation.

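### Does the predose >5% Cmax rule treat a very low fasted exposure unfairly, depending on the period in which it occurs?

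*Protocol*

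**What the plan says.** Protocol Section 7.3 (Pharmacokinetics) introduces its list with "Plasma concentrations and/or parameters of a subject will be considered as non-evaluable, if for example". One item is that "A predose concentration is" more than 5% of the Cmax "value of that subject". Flagged data are listed individually, left out of the statistics, and the exclusion is documented in the trial report. The PKS definition lets a subject contribute as little as one parameter from one period.

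SAP 7.4.1 restricts every PKS analysis to unflagged parameters and names four ratios: C/A, E/A, B/C and D/E. SAP 7.4.2 plans one sensitivity analysis, the same model with all effects fixed. SAP 6.6 refers PK outliers to a BI standard.

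On carry-over, Protocol Section 3.1 states: "There will be a washout period of at least 17 days between the treatments". Section 3.2 gives a terminal half-life "between 54.8 and 82.5 h) resulting in a long washout period (17 days"); Section 1.2.1.5 gives a shorter one: "Half-life as calculated from these 3 DGs is around 45 to 52 h (gMean"). Section 1.2.2 adds: "The Residual Effect Period (REP) of BI 1358894 is approximately 14 days".

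Table 1.2.1.5: 3 shows the 100 mg fasted Cmax with and without one low subject: "94.3 (735) 206 (72.8"), for N=6 and N=5.

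**The concern.** If the 5% refers to the same period's Cmax, the rule depends on the outcome: the lower the exposure, the more easily any carry-over crosses the threshold. Period 1 has no earlier dose, so the rule cannot act there. By Table 3.1, with two subjects per sequence, C is given 6/4/4 times in Periods 1/2/3 and E 4/6/4 times. The same event would then be open to removal in 8 of 14 C doses and 10 of 14 E doses. Fed periods are practically immune, since a Cmax of 517 nmol/L needs a predose above 26. The rule therefore bears on fasted TF2, which enters all four ratios.

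The trial looks for a formulation with little food effect and better fasted exposure, so a near-absent fasted exposure on TF2 would be a result of interest. Whether it shows in the ratios would depend on its period, and no analysis with and without it is planned.

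**Working it through.** **1. The low first-in-human subject** (Table 1.2.1.5: 3, 100 mg fasted). Low value = exp(6 ln gMean(N=6) − 5 ln gMean(N=5)).

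- Cmax (94.3; 206): 1.9 nmol/L, or 0.9% of 206.
- AUC0-tz (2520; 7120): 14.0 nmol·h/L, or 0.2% of 7120.

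Check against the printed N=6 gCV for Cmax. The log variance in the other five is ln(1 + 0.728²) = 0.425. The distance is ln(206/1.9) = 4.69. The N=6 log variance is (4 × 0.425 + (5/6) × 4.69²)/5 ≈ 4.00, so gCV = √(e^4.00 − 1), about 733% (printed 735%). The same steps for AUC0-tz give 2683% (printed 2670%). The reconstruction holds.

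**2. Carry-over 17 days (408 h) after a 100 mg dose.** Areas are from Table 1.2.1.5: 4, assuming one exponential after 72 h and TF2 like TF1: C408 = (AUC0-∞ − AUC0-72) × (ln 2/t½) × 2^(−336/t½).

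- After fed: 17200 − 11600 = 5600, so C408 = 0.49 (t½ 45 h) to 2.80 nmol/L (82.5 h).
- After fasted: 6930 − 4600 = 2330, so C408 = 0.20 to 1.16 nmol/L.

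Using the area beyond tz instead (17200 − 15500 = 1700 for fed, tz assumed 192 to 312 h) gives 0.9 to 6.4 nmol/L after a fed dose, so the rule triggers more easily.

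**3. Does the rule trigger?**

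- Usual fasted Cmax of 210: 0.49/210 = 0.2% to 2.80/210 = 1.3%. Kept.
- Low Cmax with carry-over added, after fed: 0.49/(1.9 + 0.49) = 20% to 2.80/(1.9 + 2.80) = 60%. Removed.
- Low Cmax after fasted: 10% to 38%. Removed.
- Threshold: 20 × C408, about 10 to 56 nmol/L after a fed dose.

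**4. Effect on the ratios.** The planned model was fitted to Table 3.1 (24 subjects, 72 observations) with one value shifted by ln(1.9/206) = −4.69.

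| Low Cmax value | vs A | Food effect |
|---|---|---|
| C, Period 1, kept | C/A × 0.69–0.77 | B/C × 1.26–1.44 |
| E, Period 1, kept | E/A × 0.66–0.67 | D/E × 1.30–1.49 |
| C or E, Period 2 or 3, removed | about × 1.00 | about × 1.00 |

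Simulated with gCV 25% and true ratios of 100%, a low C value kept in Period 1 gives C/A 71% (90% CI 48–107%); removed in Period 2 or 3, 100% (84–118%).

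**5. What the Period 2–3 value would contain.** Carry-over adds C408 × (t½/ln 2) × (1 − 2^(−312/t½)) to the area over 312 h, if it stays quantifiable.

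- After fed: 31 (45 h) to 309 nmol·h/L (82.5 h).
- Against a true 14: 31/45 = 69% to 309/323 = 96% of the recorded AUC0-tz would come from the previous treatment.
- Against a usual fasted AUC0-tz of 6320: 0.5% to 4.9%.

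If such AUC values were kept, the C/A multiplier would be about 0.64 to 0.84 in Periods 2–3, depending on half-life and sequence, against about 0.61 to 0.71 for a clean value of 14 in Period 1. Keeping the later value does not give equal treatment across periods.

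**6. How often?** Fasted TF1 was given to 42 + 20 = 62 subjects in the first-in-human trial, with one such value (exact 95% CI 0.04–8.7%). Among the 12 food-effect subjects at 100 mg fasted, one value 4.69 log units below the other 11 would alone contribute (11/12) × 4.69²/11 = 1.83 to the log variance, a gCV of at least √(e^1.83 − 1) = 229%. The printed gCV is 38.8%, so it did not recur there. No rate for TF2 is given.

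**The case for a change.** The best argument for acting is that, for Cmax, contamination is not what moves the answer. Keeping the Period 2–3 Cmax with its carry-over gives a simulated C/A of 73–76%, close to the 71% from Period 1; deleting it gives 100%. Non-evaluability is settled during data analysis in an open-label trial, so the denominator should be fixed beforehand. A threshold of 5% of the treatment's geometric mean Cmax (10.5 nmol/L on TF1 fasted figures) would treat all periods alike.

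The Cmax figures stand. The proposal fails on the co-primary AUC0-tz: with carry-over of 0.5 to 2.8 nmol/L it would keep areas that are mostly the previous treatment's drug. It also leaves open whether that geometric mean includes the low value, which moved it from 206 to 94.3 in the first-in-human trial.

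The unnamed Cmax is a gap in wording. Since data enter the PKS by period, and a predose sample is tested for its bearing on the profile that follows it, the same period's Cmax is the natural reading. The difference between 8 and 10 of 14 doses is two administrations, conditional on a rare event, and no E/C comparison is planned.

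Protocol Section 7.7 also quotes the Cmax gCV range as 13.4% to 72.8% without saying that 735% is left out. That is clerical, because the table it cites prints both columns with a footnote.

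**Conclusion.** No change follows. The two values being compared are not the same measurement. The Period 1 value can be attributed wholly to the dose under test; the Period 2–3 value cannot, and for AUC0-tz after a fed dose it would be mostly previous-treatment drug. The rule separates them on that ground while letting usual fasted periods through.

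The asymmetry arises only if four things hold together: the same-period reading; a predose still quantifiable on Day 17, although measurable levels are expected for about 14 days and the assay limit is not stated; usual exposure in the preceding period, since a subject who absorbs little every time carries over little; and recurrence on TF2. If it did arise, a reader would see it, because excluded values are listed, exclusions are documented in the report, and each parameter carries an inclusion flag and comment. When the event occurred in the first-in-human trial, the sponsor reported results with and without the subject, and nothing in this plan prevents doing so again. The aim is exploratory estimation without an acceptance range, so no formal decision turns on one excluded value, even though it could shift a ratio by about 25 to 35%.

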#### **7.3.1 Primary endpoint analyses**

##### Primary analyses

The statistical model used for the analysis of the primary endpoints will be an analysis of variance (ANOVA) model on the logarithmic scale. That is, the PK endpoints will be log-

Proprietary confidential information © 2019 Boehringer Ingelheim International GmbH or one or more of its affiliated companies

transformed (natural logarithm) prior to fitting the ANOVA model. This model will include effects accounting for the following sources of variation: sequence or block, subjects within sequences, period and treatment. The effect 'subjects within sequences' will be considered as random, whereas the other effects will be considered as fixed. The model is described by the following equation:

$$y_{ijkm} = \mu + \zeta_i + s_{im} + \pi_j + \tau_k + e_{ijkm}, \text{ where}$$

$y_{ijkm}$  = logarithm of response measured on subject m in sequence i receiving treatment k in period j,

$\mu$  = the overall mean,

$\zeta_i$  = the  $i^{\text{th}}$  sequence or block effect,  $i = 1, 10$ ,

$s_{im}$  = the effect associated with the  $m^{\text{th}}$  subject in the  $i^{\text{th}}$  sequence,  
 $m = 1, 2, \dots, n_i$

$\pi_j$  = the  $j^{\text{th}}$  period effect,  $j = 1, 2, 3$

$\tau_k$  = the  $k^{\text{th}}$  treatment effect,  $k = 1, 2, \dots, 5$

$e_{ijkm}$  = the random error associated with the  $m^{\text{th}}$  subject in sequence i who received treatment k in period j.

where  $s_{im} \sim N(0, \sigma_B^2)$  i.i.d.,  $e_{ijkm} \sim N(0, \sigma_W^2)$  i.i.d. and  $s_{im}$ ,  $e_{ijkm}$  are independent random variables.

Point estimates for the ratios of the geometric means (test/reference) for the primary endpoints (see [Section 2.1.2](#)) and their two-sided 90% confidence intervals (CIs) will be provided.

For each endpoint, the difference between the expected means for log(T)-log(R) will be estimated by the difference in the corresponding adjusted means (Least Squares Means). Additionally their two-sided 90% confidence intervals will be calculated based on the residual error from the ANOVA and quantiles from the t-distribution. These quantities will then be back-transformed to the original scale to provide the point estimate and 90% CIs for each endpoint.

### 7.3.2 Secondary endpoint analyses

The secondary endpoints (refer to [Section 2.1.3](#)) will be calculated according to the BI SOP 'Standards and processes for analyses performed within Clinical Pharmacokinetics/ Pharmacodynamics' ([001-MCS-36-472](#)) and will be assessed statistically using the same methods as described for the primary endpoints.

### 7.3.4 Safety analyses

Safety will be analysed based on the assessments described in [Section 2.2.2.2](#). All treated subjects (TS, refer to [Section 7.2](#)) will be included in the safety analysis. Safety analyses will be descriptive in nature and based on BI standards. No hypothesis testing is planned.

For all analyses, the treatment actually administered (= treatment at onset) to the subject will be used (any deviations from the randomised treatment will be discussed in the minutes of the Report Planning Meeting).

Treatments will be compared in a descriptive way. Tabulations of frequencies/proportions will be used to evaluate categorical (qualitative) data, and tabulations of descriptive statistics will be used to analyse continuous (quantitative) data.

Measurements (such as ECG, vital signs, or laboratory parameters) or AEs will be assigned to treatments (see [Section 4.1](#)) based on the actual treatment at the planned time of the measurement or on the recorded time of AE onset (concept of treatment emergent AEs). Therefore, measurements planned or AEs recorded prior to first intake of trial medication will be assigned to the screening period, those between first trial medication intake and end of REP (see [Section 1.2.2](#)) will be assigned to the treatment period. Events occurring after the REP but prior to next intake or end of trial termination date will be assigned to 'follow-up'. In case of two or more treatments, the follow-up will be summarized according to the previous treatment. These assignments including the corresponding time intervals will be defined in detail in the TSAP. Note that AEs occurring after the last per protocol contact but entered before final database lock will be reported to Pharmacovigilance only and will not be captured in the trial database.

Additionally, further treatment intervals (analysing treatments) may be defined in the TSAP in order to provide summary statistics for time intervals, such as combined treatments, on-treatment totals, or periods without treatment effects (such as screening and follow-up intervals).

Adverse events will be coded using the Medical Dictionary for Regulatory Activities (MedDRA). Frequency, severity, and causal relationship of AEs will be tabulated by treatment, system organ class, and preferred term. SAEs, AESIs (see [Section 5.2.6.1](#)), and other significant AEs (according to ICH E3) will be listed separately.

Proprietary confidential information © 2019 Boehringer Ingelheim International GmbH or one or more of its affiliated companies

Previous and concomitant therapies will be presented per treatment group without consideration of time intervals and treatment periods.

Laboratory data will be compared to their reference ranges. Values outside the reference range as well as values defined as possibly clinically significant will be highlighted in the listings. Additionally, differences from baseline will be evaluated.

Vital signs or other safety-relevant data will be assessed with regard to possible on-treatment changes from baseline.

Relevant ECG findings will be reported as AEs.

